The total duration of this randomized, double-blind, placebo-controlled trial will be 2 years. For each participant the total duration of the study will be 14 weeks, including 8 weeks of intervention with SXB or PBO, preceded by a 4-week period of collection of baseline data, and followed by a 2-week period of data collection post-intervention. Subjects taking MLT or any other medication capable of affecting RBD other than clonazepam (CLZ) will maintain their regimen at fixed dose throughout the 14-week duration of the study. Those taking CLZ will proceed to reduction and discontinuation of CLZ, followed by a 2-week washout period prior to receiving study drug. If unable to discontinue CLZ prior to study drug, they will reduce CLZ to lowest acceptable dose by the end of the 4-week baseline period followed by cross-taper with SXB during the first 2 weeks of flexible dosing.

In each arm, dosage of SXB and PBO will be titrated up weekly (this weekly titration will occur via phone calls by the PI on days 2-6 after each new dose change) by up to 1.5g nightly dose increments from an initial 4.5g total nightly dose (which could be given

in two unequal doses if needed, or one single dose no greater than 4.5g) to an optimal individual dose based on clinical response on RBD symptoms and tolerability, to a maximum nightly dose of 9g ("flexible dose" period lasting up to 8 weeks). The optimal dose for each participant will then be continued for at least 4 weeks ("stable dose").

Flowchart

MOCA: Montreal Cognitive Assessment

PSG: Polysomnography

CGI: Clinical Global Impression questionnaires

- **Day 1 (Visit #1 = Initial visit with research coordinator):**
 - Verification of inclusion and exclusion criteria
 - Enrollment (if not performed prior)
 - Physical Exam (MoCA,
 - PSQI, PHQ-9, GAD-7, SCOPA-AUT, Epworth sleepiness scale
 - provide RBD logs and sleep diary for the 14 following weeks, 2 blank Karolinska scales, and two actigraphy devices (Philips Actiwatch2) to be worn on dominant wrist and ankle for one month

- instructions on when to complete Karolinska scale #1 (Day 21-27, one hour after waking up the day prior to sleep study) from home
 - Instructions on clonazepam taper, when applies
 - pregnancy testing for female subjects of childbearing age, when applicable
 - collection of adverse events (AEs)
 - MD (PI, coPI) will be available as needed via telephone or remote video conference system

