- **Day 1-28 (phone calls, weekly, when applicable):** guidance on downtitration of CLZ
- **Day 28 ± 7 days:** 1st video-PSG wearing home actigraphy device (Philips Actiwatch2) and additional wrist and ankle high-frequency actigraphy device (Xiaomi Amazfit Arc)
- **Day 29 (One day after Day 28 ± 7 days, Visit #2 = Randomization visit with research coordinator):**
 - Collection of 1-month RBD log and sleep diary
 - Collection of Karolinska scale #1
 - Collection of all actigraphy devices
 - Epworth sleepiness scale
 - Randomization
 - Subjects receive SXB or PBO and instructions on titration schedule
 - pregnancy testing for female subjects of childbearing age, when applicable
 - collection of adverse events (AEs)
 - MD (PI, coPI) will be available as needed via telephone or remote video conference system

Day 30-84 ± 7 days (phone calls): Every week after each new dose the subject will be called (including when the dose will remain stable), these phone calls will be made between day 2-6 to discuss response, record adverse events, and determine the next weeks titration dose.

- **Day 57-85 ± 7 days (Visit #3 = Interim visit with research coordinator):**
 - Collection of 1-month RBD log and sleep diary
 - Epworth sleepiness scale
 - PSQI, PHQ-9, GAD-7
 - Completion of CGI-E by participants
 - Completion of CGI-I by clinician
 - Physical Exam (including MoCA, orthostatic vital signs)
 - instructions on when to complete Karolinska scale #2 (Day 78-84, one hour after waking up the day prior to sleep study) from home
 - Participants provided with two actigraphy devices (Philips Actiwatch2) to be worn on dominant wrist and ankle for one month
 - pregnancy testing for female subjects of childbearing age, when applicable

- Collection of AEs, side effects
- MD (PI, coPI) will be available as needed via telephone or remote video conference system

- **Day 84-112 ± 7 days: 2nd video-PSG wearing home actigraphy device (Philips Actiwatch2) and additional wrist and ankle high-frequency actigraphy device (Xiaomi Amazfit Arc)**

- **Day 85-113 (One day after Day 84-112 ± 7 days, Visit #4 = Final Visit with research coordinator):**
 - Collection of high-frequency actigraphy device (Xiaomi Amazfit Arc)
 - Collection of 1-month RBD log and sleep diary
 - Collection of AEs, side effects
 - Collection of Karolinska scale #2
 - Epworth sleepiness scale
 - PSQI, PHQ-9, GAD-7, SCOPA-AUT
 - Completion of CGI-E by participants
 - Completion of CGI-I by clinician

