 - Physical Exam (including MoCA,
 - Verification of any protocol deviation (e.g., change in drug regimen that could affect RBD outcome)
 - Discontinuation of treatment
 - MD (PI, coPI) will be available as needed via telephone or remote video conference system

- **Day 99-127 ± 7 days (Visit #5 = Follow-up Visit with research coordinator):**
 - Collection of AEs
 - Collection of actigraphy devices
 - Collection of 2-week RBD log and sleep diary
 - Compensation
 - End of study
 - MD (PI, coPI) will be available as needed via telephone or remote video conference system

Treatment Regimen

Being diagnosed with "refractory RBD", all participants will have received and failed prior treatments with CLZ and MLT prior to being eligible for the study. Treatment failure is defined as insufficient efficacy, or intolerance to treatment limiting the possibility of uptitration or leading to discontinuation, resulting in persistent of RBD episodes averaging 2 per week or 8 per month or greater.

At study entry, we expect most participants to currently be treated with CLZ and/or MLT. Subjects taking MLT or any other medication capable of affecting RBD other than CLZ will maintain their regimen at fixed dose throughout the 14-week duration of the study. In subjects treated with CLZ, CLZ will be titrated down and discontinued 2 weeks prior to start of study drug, or when unable to be discontinued, cross-tapered during the first 2 weeks of receiving study drug until reaching the lowest possible CLZ dose, which will then be continued until the end of the stable dosing period

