- In individuals without a diagnosis of Parkinson's disease (PD), PSG-confirmed “definite RBD” per the International Classification of Sleep Disorders, 3rd edition (ICSD-3)
- In individuals with a diagnosis of PD, either PSG-confirmed diagnosis of RBD ("definite RBD") or history of dream-enactment ("probable RBD")
- RBD episodes ≥ 2 /week or ≥ 8 /month (defined as vocalization and/or limb or body movements attributed to dream-enactment)
- Reliable reporting by bed witness in the absence of patient awareness

Exclusion Criteria

- History of falls during ambulation in the last 6 months despite adequate neurologic treatment
- Requirement of an ambulatory device at home
- Inadequately treated symptomatic orthostatic hypotension (syncopal episode in the last 6 months)
- BMI > 35
- Untreated or uncontrolled OSA (4% desaturation AHI>15)
- Liver impairment
- Renal impairment
- Congestive heart failure
- Uncontrolled hypertension
- Treatment with valproic acid
- Current history of NREM parasomnias or parasomnia overlap syndrome (at least 2 episodes in the last 6 months)
- Diagnosis of narcolepsy
- Cognitive impairment resulting in inability to comply with treatment instructions
- Diagnosis of any dementia including dementia with Lewy bodies
- Diagnosis of multiple system atrophy
- RBD attributed to a CNS lesion
- PD Hoehn and Yahr stage 4 and 5
- Any change of PD regimen during the study period
- Current alcoholism or prior history of drug abuse
- Pregnancy
- Epilepsy currently treated with sedating antiepileptic drugs;
- Concomitant use of other CNS depressants, including but not limited to opioid analgesics, benzodiazepines other than clonazepam, muscle relaxants, and/or illicit CNS depressants
- Current depression (at least PHQ-9 score = 10), history of psychosis
- Any change of antidepressant regimen during the study period
- Chronic severe RLS (iRLS>20) (at least 3 days per week)
- Succinic semi-aldehyde dehydrogenase deficiency (SSADH)

Primary Endpoint

- Number of RBD episodes in one month (RBD log), last month of treatment compared to 1-month baseline

Secondary Endpoints

- Severity of RBD episodes in one month (RBD log), last month of treatment compared to 1-month baseline. Severity is scored from 1 to 3 (1: least severe, 3 most severe):

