Sodium Oxybate in Treatment-Resistant REM Sleep Behavior Disorder (RBD): A Randomized Placebo-Controlled Trial

Statistical Analysis Plan

NCT04006925

January 11, 2023

Statistical analysis (using SAS 9.4, Cary, NC) was by intention-to-treat for the primary efficacy analysis, comparison of baseline characteristics, safety and tolerance and per-protocol (PP) for secondary/exploratory analyses. PP analysis included all participants who completed titration and the 4-week treatment period. Sample size calculation was based on a prior randomized controlled study by Brunetti et al.²⁵ To detect an effect size of 50% reduction in the number of RBD episodes per month ([placebo - active] / placebo) with a power of 80% and alpha of 5%, the number of participants needed to be 10 per arm. Anticipating a dropout rate of 20%, 24 participants required to be enrolled.

We tested the primary hypothesis that SXB is superior to placebo in reducing the number of RBD episodes from baseline, as observed in the last month of treatment using linear mixed effects models with random intercepts. Models were parameterized in two ways to estimate separate group trajectories and between-group differences in change over time. Cohen's d was calculated as a measure of treatment effect size. Similar hypotheses were tested on secondary and exploratory outcomes. Within- and between-group differences were assessed with paired- and unpaired t-tests, or with the Wilcoxon Signed Rank and Mann-Whitney U tests for nonnormal data. Bootstrapped percentile-based 95% confidence intervals were calculated based on 10,000 randomly resampled datasets. Participants scoring below 4 on the CGI-I and CGI-E were classified as "responders"; chi-square tests were performed to compare the proportion of responders between groups. All statistical tests were conducted using a 2-sided alpha level of 0.05. For secondary/exploratory analyses, bootstrapped percentile-based 95% confidence intervals were calculated based on 10,000 randomly resampled datasets. Descriptive statistics on safety data are provided for all randomized participants (intention-to-treat), by treatment group and study phase.

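### The baseline month for the primary count coincides with the clonazepam taper and washout, so within-arm change in clonazepam users mixes study-drug effect with clonazepam withdrawal

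*Protocol*

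**What the plan says.** The Primary Endpoint section of the protocol sets the outcome as "Number of RBD episodes in one month (RBD log), last month of treatment compared to 1-month baseline". Under Trial Design, study drug is "preceded by a 4-week period of collection of baseline data". In the visit schedule (Flowchart), RBD logs are issued on Day 1 and the first month's log is collected on Day 29, the randomisation visit.

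The same 28 days hold the clonazepam (CLZ) withdrawal. Visit 1 lists "Instructions on clonazepam taper, when applies", and weekly calls over Days 1–28 give "guidance on downtitration of CLZ". Trial Design states: "Those taking CLZ will proceed to reduction and discontinuation of CLZ, followed by a 2-week washout period prior to receiving study drug". With study drug dispensed on Day 29, a two-week washout fills about Days 15–28 and leaves about Days 1–14 for the taper. For participants who cannot stop, "they will reduce CLZ to lowest acceptable dose by the end of the 4-week baseline period followed by cross-taper with SXB". Treatment Regimen then has them continue a residual dose to the end of stable dosing. Melatonin and other RBD drugs are held fixed; CLZ is the stated exception.

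On how many are affected, Treatment Regimen says only: "At study entry, we expect most participants to currently be treated with CLZ and/or MLT". No share for CLZ alone is given.

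The SAP uses a linear mixed model with random intercepts and adds: "Models were parameterized in two ways to estimate separate group trajectories and between-group differences in change over time". Neither document limits the baseline to particular nights, stratifies randomisation by CLZ use, or names a CLZ covariate or sensitivity analysis.

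**The concern.** A change score is interpretable when background treatment is the same at both ends. For a CLZ user who stops, the baseline month mixes nights on a falling dose with nights off the drug, while the last treatment month is off it. A user who cannot stop logs the whole baseline on falling CLZ and is then compared with a month at a lower residual dose. Non-users have a stable background throughout.

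If CLZ was still giving some benefit, users' baselines are too low. Improvement on sodium oxybate (SXB) is then understated, and placebo users appear to worsen because a treatment was withdrawn. If stopping CLZ causes rebound episodes during the washout, the baseline is too high and the error runs the other way. A reader of the two trajectories could not separate either effect from the effect of study drug. In addition, with 12 per arm and no stratification, a chance excess of users in one arm shifts the estimated difference in change.

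**Working it through.** **1. The plan's own figure.** From the protocol's sample size section, the difference is 0.5 × 10.3 = 5.15 episodes per month; the SD is taken as 3.7 (the follow-up placebo value), with two-sided alpha 5% and power 80%. Then n = 2(1.96 + 0.84)² × 3.7² / 5.15² = 8.1, rounded up to 9 per arm. The t-based version gives 9.17, rounded up to 10. The stated 10 per arm reproduces. It contains no allowance for CLZ.

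**2. Baseline in a user who stops.** Assumptions, since the documents give no figures: 16 episodes per 28 nights off CLZ, 8–12 on CLZ, 14 taper nights, 14 washout nights, no rebound. Baseline = ½ × (mean rate during taper) + ½ × (off rate). With a linear taper, the mean taper rate is midway between the on and off rates.

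| On-CLZ count | First 14 nights | Logged baseline | Placebo user staying at 16 | User falling to 8 |
|---|---|---|---|---|
| 12 | linear taper | ½×14 + ½×16 = 15 | +1/15 = +7% | −7/15 = −47% |
| 8 | linear taper | ½×12 + ½×16 = 14 | +2/14 = +14% | −6/14 = −43% |
| 12 | full effect | ½×12 + ½×16 = 14 | +14% | −43% |
| 8 | full effect | ½×8 + ½×16 = 12 | +4/12 = +33% | −4/12 = −33% |

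The linear rows match a falling dose; the full-effect rows are an upper case. In general, if CLZ removes a fraction e of episodes, the baseline is low by e × f, with f = 0.25 (linear) or 0.5 (full effect). For e from 20% to 80%, the linear case gives a baseline 5–20% low and an unchanged placebo user reading 5–25% worse.

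**3. Between-arm contrast.** Linear case, baseline 14: SXB changes by 8 − 14 = −6 and placebo by 16 − 14 = +2, a difference of −8. Upper case, baseline 12: −4 and +4, again −8. Both equal 8 − 16. The baseline error cancels when users are balanced between arms.

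**4. Precision.** Take the protocol's SDs of 5.2 and 3.7 with an assumed correlation r of 0.5. The SD of change is √(5.2² + 3.7² − 2×0.5×5.2×3.7) = √21.49 = 4.64. A drift d in a share p of participants adds p(1−p)d² to the variance. With p = 0.5, the share at which this term is largest:

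- d = 1: √(21.49 + 0.25) = 4.66
- d = 2: √(21.49 + 1.00) = 4.74
- d = 4 (upper case): √(21.49 + 4.00) = 5.05

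The increases are 0.6%, 2.3% and 8.9%. For d = 2, r = 0.3 gives √29.19 to √30.19 (+1.7%), and r = 0.7 gives √13.79 to √14.79 (+3.6%).

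**5. Chance imbalance, the same effect seen another way.** The SD of the shift in the between-arm difference is d√(0.25 × 2/12) = 0.20, 0.41 and 0.82 episodes for d = 1, 2 and 4. This is the step 4 variance term carried into the standard error; for d = 4, √(4.64² × 2/12 + 0.82²) = 2.06 = 5.05 × √(2/12). It must not be added on top. If 12 of 24 are users, the hypergeometric probability that the arms differ by four or more users is 22%. A difference of four moves the contrast by d × 4/12 = 0.33, 0.67 or 1.33 episodes, against a planned 5.15.

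**6. Would a washout-only baseline be better?** Assume Poisson counts at 16 per 28 nights. A full-month count has variance 16; a 14-night count doubled has variance 4 × 8 = 32. The extra 16 in half the participants adds 8 on average, giving √(21.49 + 8) = 5.4. That exceeds every SD in step 4.

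**The case against.** The strongest objection is that the trial's question is comparative. The taper precedes randomisation and both arms go through it, so the SXB–placebo difference in change is not biased in expectation by the baseline overlap. This stands, and step 3 shows it.

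A reader might infer from step 2 that the trial would see a true 50% effect as only 33–43% and so miss its target. The documents do not support that. Both define the planned 50% as placebo minus active, divided by placebo, which is a ratio between arms. In the example it is (16 − 8)/16 = 50% whatever the baseline reads. The within-arm percentage is not what the trial was sized on, and 33–43% also requires the full CLZ effect on nights when the dose is falling.

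A second objection is that participants are refractory, so CLZ may be doing little. This stands in part. The protocol's figure of about 80% efficacy comes from a case series, not from people who had failed the drug, so large residual effects are conjecture. But Treatment Regimen counts intolerance that limits dose increases as failure, and the protocol foresees people who cannot stop, so some residual benefit is plausible.

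**Conclusion.** The timing overlap is certain from the text, as is the absence of any provision for it in the analysis. The consequence is secondary. Within-arm change in CLZ users does not measure study-drug effect alone, and the SAP's separate group trajectories inherit that. The comparison between arms loses a little precision: under the linear-taper assumptions the SD of change goes from 4.64 to 4.66–4.74, and to 5.05 at most in the upper case.

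The sizes rest on an assumed CLZ share, residual effect, taper shape and correlation, none of which the documents give. The usual direction is understated improvement, but rebound could reverse it. Nothing here shows that the primary test is invalid or the sample size wrong. The conclusion about bias covers the baseline overlap only; it does not address whether CLZ dose after randomisation differs between arms. The point merits a change to the analysis, not to the design.

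**What to change.** Add CLZ use at entry (yes/no) and its interaction with time to the primary mixed model. Report group trajectories separately for users and non-users, and show participants who could not stop CLZ as their own group. The taper procedure already requires entry use to be known, so this needs no new data.

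Keep the full-month baseline as primary. A baseline limited to nights after discontinuation, scaled to 28 nights, should be a sensitivity analysis only. It is noisier (step 6), does not apply to those who cannot stop, and needs CLZ stop dates, which the documents do not say are recorded. The taper itself need not change.

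The cost is a few lines in the SAP and one or two extra model terms with 24 participants. If the CLZ effect is small, the gain in precision may be slight; the main benefit is trajectories that can be interpreted. The SAP is written in the past tense, so if the primary analysis has already been run, the adjusted model should be reported as a labelled sensitivity analysis.

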Sodium Oxybate in Treatment-Resistant REM Sleep Behavior Disorder (RBD): A Randomized Placebo-Controlled Trial

Statistical Analysis Plan

NCT04006925

January 11, 2023

Statistical analysis (using SAS 9.4, Cary, NC) was by intention-to-treat for the primary efficacy analysis, comparison of baseline characteristics, safety and tolerance and per-protocol (PP) for secondary/exploratory analyses. PP analysis included all participants who completed titration and the 4-week treatment period. Sample size calculation was based on a prior randomized controlled study by Brunetti et al.²⁵ To detect an effect size of 50% reduction in the number of RBD episodes per month ([placebo - active] / placebo) with a power of 80% and alpha of 5%, the number of participants needed to be 10 per arm. Anticipating a dropout rate of 20%, 24 participants required to be enrolled.

We tested the primary hypothesis that SXB is superior to placebo in reducing the number of RBD episodes from baseline, as observed in the last month of treatment using linear mixed effects models with random intercepts. Models were parameterized in two ways to estimate separate group trajectories and between-group differences in change over time. Cohen's d was calculated as a measure of treatment effect size. Similar hypotheses were tested on secondary and exploratory outcomes. Within- and between-group differences were assessed with paired- and unpaired t-tests, or with the Wilcoxon Signed Rank and Mann-Whitney U tests for nonnormal data. Bootstrapped percentile-based 95% confidence intervals were calculated based on 10,000 randomly resampled datasets. Participants scoring below 4 on the CGI-I and CGI-E were classified as "responders"; chi-square tests were performed to compare the proportion of responders between groups. All statistical tests were conducted using a 2-sided alpha level of 0.05. For secondary/exploratory analyses, bootstrapped percentile-based 95% confidence intervals were calculated based on 10,000 randomly resampled datasets. Descriptive statistics on safety data are provided for all randomized participants (intention-to-treat), by treatment group and study phase.

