Participants will be randomized in a double-blind manner to either SXB or PBO. The duration of the intervention in both conditions will be no longer than 12 weeks, including up to 8 weeks of flexible dosing and 4 weeks of stable dosing. Treatment will be initiated with 4.5g dose of SXB or PBO, given nightly in two doses 2.5-4h apart according to the standard protocol used in narcolepsy. PBO will be similar in appearance, smell and flavor to the subjects, so that the investigators and participants will be unable to distinguish it from SXB. The dose will be increased or decreased by 0.5 - 1.5g weekly increments until reaching the optimal dose based on clinical response and tolerance, not exceeding 9g nightly. Evidence has shown that patients with RBD treated with sodium oxybate respond to nightly doses ranging from 3-6 g. Among these subjects, some have benefited from a 5 gram nightly dose. This flexibility in dosage is determined on an individual basis, in which the final dose must be both effective and tolerated. Dosage flexibility is essential as this older population with prodromal or overt signs of neurodegeneration may not require or tolerate the higher dosages used in patients with narcolepsy. Although the “default” regimen will be two equally divided doses 2.5-4hours apart, if required, the drug will be given in two unequal doses, or in one single dose, with no single dose allowed to be greater than 4.5g. Once optimal dose reached, fixed dose will be continued for at least 4 weeks and discontinued over one night. During the two weeks following discontinuation, data will continue to be collected. Patients will be allowed to resume usual treatment, including CLZ.

In this study, the choice of flexible dosing for patients receiving SXB is based on a few factors. From the 4 case reports summarized above, effective doses of SXB in patients with refractory RBD ranged from 3g to 6g nightly, one patient requiring uptitration of his initial 5g dose to 6g. No adverse events or side effects were reported by the authors. In patients with narcolepsy, the efficacy of SXB is dose-dependent, showing superior efficacy with 9g nightly dose compared to 6g. Taken together, this data suggests that higher SXB doses will be more likely to control RBD symptoms, however with a higher risk of side effects. In the two studies evaluating SXB efficacy and tolerance in patients with PD using flexible dosing, final mean doses were 7.8g and 4.8g^{14,15}.

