Our study will include a mixed group of participants, some with a neurological diagnosis of PD and some otherwise healthy individuals. We identify risk of dizziness and falls as the most concerning risk in patients with a diagnosis of synucleinopathy, as this could be aggravated by SXB. We will therefore carefully exclude from this study any participant who already suffers from balance impairment resulting in falls or requiring an ambulating device, as well as any patient with symptomatic orthostatic hypotension. Taken all these considerations into account, and given the expected interindividual variability regarding

optimal dose of SXB, we chose flexible dosing for highest clinical benefit while minimizing the risk of side effects.

The total amount of SXB for the 12 participants randomized to active drug is: 5,292g.
The total amount of PBO for the 12 participants randomized to placebo drug is: 5,292g.

Option for “Rescue” Open Label Extension Period

All participants, should they decide to drop out of the study, may become eligible for a “Rescue” open label extension period, during which they will receive open label active drug sodium oxybate in an unblinded fashion. This will provide patients the opportunity of experiencing benefit from the study drug. Such participants would then receive ascending doses of sodium oxybate, according to the protocol, and will also be asked to present for visits and second polysomnography starting at visit 2, otherwise required by the protocol until the end of the study.

Inclusion Criteria

- Adult patients aged 40 to 85 years
- Women may be included only if they have a negative β -HCG test at screen; are sterile (documented hysterectomy, bilateral oophorectomy, or bilateral salpingectomy, or congenitally sterile) or postmenopausal (no menses for 12 months without alternative medical cause).
- Women with childbearing potential whose male partners are potentially fertile must use one of the following highly effective birth control methods for the duration of the study (ie, starting at screening) and for 30 days after last dose of study drug
 - estrogen-progestin oral contraceptive pills, patches, or vaginal ring
 - progestogen pills, implant or injection
 - intrauterine device (IUD)
 - intrauterine hormone-releasing system (IUS)
 - bilateral tubal occlusion
 - vasectomised partner (the sole sexual partner who has received medical assessment of the surgical success)or
 - abstain from heterosexual intercourse

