 1. non injurious behaviors: facial expressions, non-aggressive vocalizations (mumbling, gentle talking, casual conversation, singing, laughing...), twitches, gentle shaking, non-aggressive movements of fingers, arms or legs...;

2. potentially injurious: punching, kicking, arm flailing or thrashing around, at least one limb or head out of bed, sitting up in bed, crawling, attempting to stand up or leave bed, near falls, cursing, screaming, shouting, yelling, or any behavior requiring bed partner to wake up participant;
 3. injurious: any contact with bed partner (hitting or grabbing), wall or furniture, any fall or leaving bed (doving out, walking, jumping).
- CGI efficacy scale (CGE-E): 4-point therapeutic effect scale and 4-point side effect scale, jointly filled by patient and partner on last day of treatment
 - CGI improvement scale (CGI-I): 7-point improvement scale filled by clinician on last day of treatment
 - RWAi according SINBAR criteria comparing PSG pre-intervention to PSG post-intervention
 - video-PSG analysis of REM related vocalizations and movements (“simple” versus “complex”) as per Sixel-Döring and colleagues¹⁶
 - Sleep outcomes: EDS, Karolinska 1 h after awakening

Exploratory Endpoints

- “Activity index” as recorded by actigraphy¹⁷ (percentage of 30-second epochs with an activity score above zero) last month of treatment compared to 1-month baseline
- Sleep outcomes: PSQI
- Cognitive outcome: MoCA
- Mood and Anxiety: PHQ-9 and GAD-7
- Orthostatic vital signs

Sample Size Justification/Statistical Analysis

Sample size calculation was made for the outcome of number of RBD episodes per month. Based on the data published by Brunetti et al.¹⁸, the number of RBD episodes decreased from 11.2 \pm 5.2 at baseline to 10.3 \pm 3.7 per month in the placebo arm. To detect an effect size of 50% reduction in the number of RBD episodes per month ([placebo-active]/placebo) with a power of 80% and alpha of 5%, the number of participants would need to be 10 per arm. Based on prior studies using SXB in subjects with PD, a conservative drop out rate of 15-20% could be anticipated^{14,15}, which would require to enroll at least 24 participants, i.e. 12 participants per arm.

Reporting to Jazz Pharmaceuticals

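### Secondary and exploratory efficacy outcomes are analysed only in completers, with no all-randomised analysis beside them, so dropout related to outcome that differs by arm could bias them in either direction

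*SAP*

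**What the plan says.** The SAP uses intention-to-treat for primary efficacy, the baseline comparison, safety and tolerance. For the rest it specifies "per-protocol (PP) for secondary/exploratory analyses. PP analysis included all participants who completed titration and the 4-week treatment period". It names no all-randomised analysis, missing-data rule or sensitivity analysis for those outcomes. The protocol's statistical section names no analysis set at all.

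The outcomes concerned include:
- the first secondary endpoint, "Severity of RBD episodes in one month (RBD log), last month of treatment compared to 1-month baseline";
- the CGI-E and CGI-I responder rates, for which "chi-square tests were performed to compare the proportion of responders between groups";
- RWAi, video-PSG and sleepiness;
- the exploratory outcomes.

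On dropout, the protocol's sample size section says "a conservative drop out rate of 15-20% could be anticipated", and the SAP uses 20%. The protocol's rescue section says "All participants, should they decide to drop out of the study, may become eligible for a" rescue period on open-label SXB. Such participants "will also be asked to present for visits and second polysomnography starting at visit 2". The protocol's Treatment Regimen section says "higher SXB doses will be more likely to control RBD symptoms, however with a higher risk of side effects". The Flowchart also has a blinded assessment before the final one ("Visit #3 = Interim visit with research coordinator"), at which the RBD log, ESS, PSQI, PHQ-9, GAD-7, MoCA, orthostatic signs, CGI-E and CGI-I are all collected.

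**The concern.** Restricting the analysis to people who finished treatment conditions on something that happens after randomisation and that treatment may influence. The documents suggest several routes, and they do not all point the same way:

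- SXB participants with poor outcomes leave: the completer result is too favourable to SXB.
- Placebo participants with poor outcomes leave, perhaps because open-label drug is available: the result is too unfavourable to SXB.
- SXB participants who would have responded leave because of side effects: again too unfavourable to SXB.

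Responder proportions also lose the dropouts from the denominator. At stake are the CGI, polysomnographic and sleepiness results. The protocol's summary presents combined clinical and physiological outcomes as a distinctive feature of the trial. From completer tables alone, a reader cannot tell whether there is bias or which way it runs.

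**Working it through.** **Numbers in the plan.** Placebo mean 10.3, SD 3.7, and a 50% reduction, so the difference is 5.15. Normal approximation, two-sided 5%, 80% power: n = 2 × (1.96 + 0.84)² × (3.7/5.15)² ≈ 8.1, so 9 per arm. The t-test version gives 9.17, so 10 per arm, which is the plan's figure. For dropout, 20 × 1.2 = 24 (20/0.85 also rounds up to 24; 20/0.8 = 25). Going from 24 to 20 means four people outside the completer set; at 20% dropout the expected number of completers is 24 × 0.8 = 19.2.

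**Assumptions.** The documents give no dropout by arm, no dropout-outcome relation and no CGI response rates. Every pattern below is assumed: 12 per arm, no true effect, and the participants with the highest dropout propensity removed. Here r is the correlation between propensity and a worse outcome. Negative bias favours SXB.

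**Final score, t-test on completers (simulated).**
- Two SXB-only dropouts: bias -0.14 SD (r = 0.5) to -0.22 SD (r = 0.8); type I error about 6.3-6.6% and 8.8%, the first range being simulation error.
- Two placebo-only dropouts: +0.14 to +0.22 SD; 6.4-8.5%.
- Two SXB-only dropouts who would have done better (r = -0.5): +0.14 SD; 6.4%.
- Two per arm: bias 0.00; 5.4-6.9%. With r = 0: bias 0.00; about 5%.

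**Change from baseline, three SXB-only dropouts.**
- Dropout tracks the final score (baseline-final correlation 0.3-0.7): 5.6-7.1%.
- Dropout tracks change itself: 7.5-11.8%, close to the 7.3-11.9% for a final score with three dropouts.

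**CGI responders, uncorrected chi-square, true rates 33-60% in both arms.**
- Two SXB-only dropouts under the same selection (r 0.5-0.8): 6.7-9.9%.
- Both dropouts certain to be non-responders (exact enumeration): 8.2%, 10.5% and 13.9% at rates of 33%, 50% and 60%, against 5.3%, 6.4% and 5.9% with no exclusions. The difference shifts by 6.7, 10.0 and 11.8 points.

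**Crossing 0.05.** With responders a and non-responders b on SXB, and c and d on placebo, chi-square = N(ad - bc)² / (product of the four margins).
- 8/12 v 4/12: 24 × 48² / 12⁴ = 2.67, p = 0.10. Remove two SXB non-responders, 8/10 v 4/12: 22 × 56² / (10 × 12 × 12 × 10) = 4.79, p = 0.029 (0.079 with continuity correction).
- 9/12 v 4/12: 24 × 60² / (12 × 12 × 13 × 11) = 4.20, p = 0.041. Remove two placebo non-responders, 9/12 v 4/10: 22 × 42² / (12 × 10 × 13 × 9) = 2.76, p = 0.096. If instead two SXB responders leave, 7/10 v 4/12: 22 × 44² / (10 × 12 × 11 × 11) = 2.93, p = 0.087.

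**Does an all-randomised mixed model cure it?** Three SXB-only dropouts, r = 0.8, Visit 3-final correlation 0.71-0.80. If dropout tracks Visit 3 or baseline scores, the model's bias is 0.00. If it tracks the unseen final score, the model's bias is -0.10 to -0.15 SD, against -0.09 to -0.22 SD for completer change. For those with baseline only, the model's bias is -0.16 to -0.29 SD, which is worse than completers.

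**The case against.** The primary outcome, safety and tolerance are already intention-to-treat, the completer set is openly defined, and the affected outcomes are secondary or exploratory in a 24-person trial. Losses from one arm only are a chosen extreme, and balanced loss gives about zero bias under no effect. Many secondary outcomes have baselines, and change scores are little affected when dropout tracks the final score. For polysomnography, a dropout has no final recording on blinded drug, so completers are nearly all the usable data. All of this stands. It limits the size of the problem but does not supply the missing analysis.

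Three stronger readings are tempting, and the documents do not support them:

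- **That the CGI comparison is the most fragile.** The 8.2-13.9% figures assume that every dropout is a non-responder. Under the same selection as the continuous score, the CGI range (6.7-9.9%) largely overlaps the t-test range (about 6.3-8.8%).
- **That the completer set favours SXB.** The plan's own dropout routes run both ways, and dropout by arm is not given.
- **That two dropouts overturn the chi-square whatever its form.** The SAP does not say whether a continuity correction applies. With it, 8/10 v 4/12 does not reach 0.05.

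**Conclusion.** The gap is real and cheap to close. As written, secondary and exploratory efficacy rests on completers alone, and dropout related to outcome that differs by arm could bias it in either direction. Under the assumed patterns with two dropouts from one arm, nominal 5% tests run at roughly 6-10%, or up to 13.9% for the CGI if selection is perfect.

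The statement that bias is about zero when dropout is similarly related to outcome in both arms is for no true effect. With true response rates of 60% v 30% and an average 16.7% loss per arm confined to non-responders, simulation moves the 30-point difference to 36.

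Nothing in the documents shows that bias occurred, and the primary result is untouched.

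**What to change.** Keep the stated per-protocol analysis. Add an analysis of all randomised participants as allocated, dated and labelled post hoc, since the SAP is written in the past tense.

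1. Outcomes also measured at Visit 3 (RBD log severity, ESS, PSQI, PHQ-9, GAD-7, MoCA, orthostatic signs): a mixed model using baseline and all blinded post-baseline data.
2. CGI-E and CGI-I: keep everyone randomised in the denominator and count dropouts as non-responders, stated as a treatment-failure definition. Add a sensitivity analysis that uses the blinded Visit 3 CGI where recorded and otherwise varies the assumed outcome by arm.
3. Outcomes with one post-baseline measurement (RWAi, video-PSG, PLM arousal index, Karolinska, actigraphy): label as completer-based and add a sensitivity analysis varying dropouts' assumed outcomes by arm.
4. Do not count data collected on open-label SXB as blinded data under the randomised arm.
5. Report dropout by arm and reason.

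Present the per-protocol, all-randomised and sensitivity results together. State that agreement between the first two does not by itself rule out bias: if dropout tracks the unseen final outcome, both can be wrong in the same direction.

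The cost is one more set of tables and a short addendum, with post hoc status. Response rates may look less favourable, and counting dropouts as failures penalises the arm that loses more participants.
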